1. STUDY AIM, BACKGROUND, AND DESIGN ABSTRACT

The aims of the current study are to conduct a small case series (up to N=30) to evaluate the preliminary feasibility of implementing a brief, episodic future thinking (EFT) intervention in a substance use treatment setting serving low-income parents.

Episodic future thinking (EFT) refers to the ability to imagine, in vivid detail, events that may occur in the future (Lin & Epstein, 2014). EFT relies on episodic memory, which allows for recollection of past, personal experiences. Research has shown that episodic memory supports the creation of positive, future events by combining past experiences with vivid detail of events that may occur in the future. Recent studies have shown that EFT intervention can decrease delay discounting (DD), which is a facet of impulsivity (Dassen et al., 2015; Snider et al., 2019; Stein et al., 2016).

The overarching goal of this EFT intervention is to increase parents' focus on positive, future events associated with enhancing the parent-child relationship. Rather than trying to decrease negative parenting practices, the focus of this study is to promote positive parent-child relationships by envisioning future-directed events. To date, no research has examined EFT in relation to parenting behaviors. Moreover, the intervention requires limited time and financial resources to implement, suggesting it may be effectively delivered in a disadvantaged community. The current application of EFT proposes to examine the efficacy of EFT in improving parent-child relationships in the low-resource, minority-majority community of Flint, Michigan. Results from this case series will inform a revision of the intervention with respect to dosage and feasibility outcomes.

Aims of this study include: (1) determining the implementation potential of this intervention (including feasibility, acceptability, and satisfaction) and (2a) examine preliminary efficacy of this intervention in reducing parental delay discounting (focus on immediate relative to long-term rewards) and (2b) improvements in parent-child relationships/parenting quality and related constructs.

2. SUBJECT POPULATION AND ELIGIBILITY

Up to 30 parents will be recruited to participate in this study from an inpatient substance use treatment center (Flint Odyssey House), in Flint, MI with a secondary location in Saginaw, MI ("Odyssey House" will be used from here forward to indicate both sites). This research includes individuals currently receiving inpatient substance use treatment. Individuals with substance use disorders (SUD) and those from impoverished areas are more likely to have shortened time horizons and have more difficulty picturing positive future events with their children.

Inclusion criteria:

1. Be the parent of a child between the ages of 6-10
2. Willing to participate in the study
3. Able to participate in written assessments and an intervention conducted in English
4. Are receiving services at Flint or Saginaw Odyssey House ("Odyssey House")
5. Be willing to receive daily post cards and meet regularly with a peer recovery coach over the course of two weeks following the initial intervention
6. Can legally consent for the child to take part in the study and are with their child 50% of the time.

Exclusion criteria:

1. Self-disclosed active suicidality/homicidality
2. Self-disclosed current bipolar disorder, schizophrenia, or psychosis

Children will not directly take part in the intervention; however, they will be included in the observational tasks with enrolled parents that are part of the larger assessment battery to evaluate changes in parenting. Children above age 7 will be verbally assented prior to participating in the observation.

Outside of the assent procedures, research team members will not directly interact with children that are participating in the observation. If the interested individual has more than one child in the age range (5-10 years old) we will ask them to complete the observation session with their youngest child in that age range.

In addition to parent enrollment, we will conduct up to 10 key informant interviews with stakeholders at Odyssey house, including Odyssey House leadership and peer interventionists, to obtain feedback on the intervention and any improvements that can be made.

Enrollment and/or Screening

Parent participants will be recruited using flyers displayed at the facility, announcements made at regularly scheduled resident meetings and/or approached directly to gauge interest in participating.

The Odyssey House Clinical Supervisor or other study staff (e.g., Peer) will approach potentially eligible participants to discuss the study and, if the participant expresses interest in participating, conduct the screening procedures to determine eligibility. All individuals will be informed that participation is completely voluntary, will be kept confidential, and will not impact their access to services in any way. The clinical supervisor or study staff conducting screening procedures will then document whether the participant meets eligibility criteria and record this information in the secure study REDCap database.

Once an individual expresses interest in taking part in the study and is determined to be eligible, a Peer will be assigned to approach the participant to obtain consent. The participant and the Peer will determine a time that is mutually convenient for them to conduct the consent process and initial assessment. Odyssey House is a residential treatment center; therefore, screening, consent processes, assessments and the intervention will be conducted in small, private rooms located at Odyssey House. During this scheduled meeting time, the Peer will explain the study to the participant and go through consent procedures. No data beyond eligibility will be collected prior to enrolling in the study. No medical records will be accessed as part of this study. If the interested individual does not meet inclusion/exclusion criteria (“screens out”), they will be offered a resource list of free or reduced cost resources in the Flint area.

Stakeholder Enrollment – Key Informant Interviews

Stakeholders, including peer interventionists and Odyssey House leadership/staff that were involved in the project, will be approached via phone or email or in person at Odyssey House and asked if they would be willing to take part in a one-time interview. Interested individuals will be included.

3. STUDY PROCEDURES

Study procedures will only be carried out by Odyssey House or HFH staff that are 1) adequately trained on the study protocol and procedures and 2) listed as key personnel on the IRB with documentation of completion of CITI and any applicable training requirements. Anyone that does not meet those criteria will not carry out any study procedures.

Following screening, eligible and interested parent participants will meet with a study Peer to begin consent procedures. During consent procedures, the participant will be informed that the intervention session, observation, and key informant interview will be recorded for research purposes. If the participant consents, the participant will be provided a copy of the signed consent.

After consent procedures, participants will be asked to take a pre-assessment battery. The assessment battery may be split into multiple sessions as needed based on participants' request, attention span, or time availability. The assessment battery will include measures of (1) delay discounting (DD) (**Aim 2a**), (2) consideration of future consequences (**Aim 2a**), (3) child behavior (**Aim 2b**), and (4) parenting variables (**Aim 2b**). To measure DD, we will use the Monetary Choice Questionnaire (MCQ). To assess how the participant considers the future while making decisions (both in general and with their child), using an adapted (to focus on parenting) version of the Consideration of Future Consequences Scale (CFC). To assess child behavior, we will use the Strengths and Difficulties Questionnaire (SDQ) – age 4-10, and child behavior questions from the Children's Health Questionnaire. In order to assess parenting characteristics, we will use the Aggravation in Parenting Scale (APS; a measure of parents' perceived aggravation related to parenting), the Alabama Parenting Questionnaire (APQ; a measure of different parenting behaviors), Parenting Laxness questions (from The Parenting Scale), Parent-Child Conflict Tactics Scale, Parenting Joy, and the Parenting Stress Index (PSI-4). At the last assessment only, parents will also complete a client satisfaction questionnaire (CSQ) and a Working Alliance Inventory (WAI). Additionally, the peer interventionist will complete a brief measure of their perceptions of participants' engagement in the intervention.

All questionnaires are hosted in the study's secure REDCap database will be completed on a password protected computer and encrypted, unless use of the computer is unavailable/impractical (internet outages, disruptions to REDCap, etc.) in which case participants will be able to fill out forms using paper-and-pencil. All measures have proven psychometric properties and are validated for the parents of children ages 6-10.

As soon as possible after the pre-intervention assessment is completed, if the participant's child assents to participate, we will complete a 20-minute observation that will be videotaped and led by either the peer or other study staff. Verbal child assent will be obtained from the child prior to beginning the observation and assent will be documented in REDCap. During the observation, the parent and their child will complete a clean-up, homework, and play task. The interaction will be videorecorded, and recordings will be stored on a password protected servers and accessible only to study staff. Behavior will be coded using a standardized coding procedure (the DPICS). Although the observation will only last approximately 20 minutes, we will ask to schedule these sessions for 40 minutes to allow time for child assent and instructions. All assessments (including the questionnaires and videotaped interaction) will be administered by either a Peer or by study staff, depending on Peer availability. Compensation for the pre-assessment (assessments and observation session) will be \$15.

Approximately one week after the pre-intervention assessment is completed, the participant will take part in the EFT intervention, led by a trained peer parent or the PI. The intervention session will last 75- 90 minutes in total and will be recorded for fidelity and to accurately capture each participant-generated episode. The session will begin by the PI/interventionist providing a general overview of the study and reviewing confidentiality. The participant will be asked to discuss their relationship with their child and to give examples of both positive and negative parenting from their personal experience. The interventionist will ask the participant to think about their long-term parenting goals and will discuss how to create a vivid event that will be easy to remember. Finally, several timepoints (based on important future milestones the participant identifies) will be used to create EFT events. The interventionist will create short cues from these events that will then be sent to the participant via postcard once a day for

two weeks. Cues will also be briefly discussed by the peer and participant at several points over the subsequent two weeks. The interventionist will document each check-in for tracking purposes. Peers may split the intervention into more than one meeting depending on participant need/response (related to fatigue, attention, etc.). Immediately following the intervention, parents will complete the MCQ and Parenting Joy survey again. Over the following two weeks, participants will be sent daily postcards including the cue phrase (designed to trigger recall of the future episode they identified during the intervention) and briefly meet with a peer to recall the scenes they envisioned and remind them of what they discussed during the intervention. The participant will receive \$14 at the end of two weeks for meeting regularly with the peer (between 3-7 times over the two weeks). The cumulative earned incentive amount will be paid.

Two weeks after the intervention session, participants will complete a post-assessment battery. This assessment will include the same measures as the pre-assessment battery, with the exception of the demographics and items from the Children's Health Questionnaire. Additionally, participants will complete a brief measure of intervention satisfaction and working alliance. Peer interventionists will also be asked to rate how engaged they felt the participant was during the intervention. The post-assessment will also include a second observation session with the parent and the same child with similar tasks to the initial observation session. Participants will be given \$15 for completing the post-intervention assessment.

Following completion of the intervention, participants will also be given an opportunity to receive an additional \$15 for taking part in a 30-minute key informant interview (KII; see KII script) that gauges participants' views on their perceived acceptability and satisfaction with the intervention and study processes. These interviews will be audio-recorded; recordings will be kept on secure servers, accessible only to the study team, and deleted after 3 years. Participants will receive \$15 for completion of the KII.

After completing all study procedures, all participants will be offered a resource guide of free and low- cost resources in the Flint area.

Thus, in total, there will be four study visits/interactions: (1) the initial (baseline) assessment; (2) the intervention; (3) the post-intervention assessment; and (4) the key informant interview (which may be completed over the phone, based on participant preference).

The interventions will be conducted by peer parents. These will be individuals who are already employed by the agency and are certified as peer recovery specialists by the State of Michigan. Agency and center staff will identify peer parents who would be appropriate to engage in this work. Peer parents will then be approached and asked if they are interested; they will be informed that working on this study is optional and that their employment is not contingent on participation. These procedures were created in conjunction with leadership from Odyssey House and peers' time will be supported by grant funding. Peers will be trained by the PI ([name]) and provided weekly and as-needed supervision, including individual review of taped session for fidelity and training purposes. All recordings of peer- participant interactions will be stored on password protected servers and will be destroyed following the three-year requirement for data storage. All peer parents (once selected) will be added to the IRB as research assistants and complete all required human subjects training. We elected to utilize peer parents given strong evidence that peers are perceived as less stigmatizing and, with training, are able to implement straight-forward interventions with fidelity.

In the event that a parent is discharged from, leaves Odyssey House after enrollment, or needs to pause study procedures for another reason, the parent will not automatically be withdrawn from the study and will be allowed to continue in the study if they wish. For those that have left Odyssey House and want to continue, we will work with the parent to determine a convenient location to complete the study.

procedures (e.g., another Odyssey House facility, their home, another residential center, etc.). In some circumstances, parents may leave Odyssey House without warning and, since we don't have their contact information, would essentially be lost to follow up unless they return to Odyssey House.

Their data would remain in the study for any study procedures that were completed prior to discharge/leaving unless they ask to be withdrawn from the study. If the parent leaves and returns to Odyssey House and wants to resume the study, study procedures can resume. For anyone in which there is a long pause in study procedures (due to discharge or other reasons), we would potentially ask the parent to retake the baseline assessments or other study procedures if an extended period of time has passed since initial completion.

We estimate that it will take 2-4 months to recruit and train peer parents, 2-4 months for recruitment of participants, 2-4 months for running the study, and 2-4 months for project wrap-up and data analysis from the time of grant award.

Additional Information:

*This project is currently funded by an award from NIDA/ NIH.

*Since this is a pilot feasibility study, the sample size was selected to provide sufficient information regarding implementation outcomes and detect signal on outcomes. Findings from this project will be used to adapt the intervention for a larger RCT.

*The PI will conduct all analyses. She received a minor-specialization in qualitative methods as part of her doctoral studies and serves as the statistical consultant on two NIH-funded treatment development grants.

Weeks from Enrollment	1	2	3	4	5-6
Activity	Assessment 1 (surveys and observation)	Intervention (+MCQ and Parenting Joy survey)	Daily postcard messages and regular (3-7) check-ins with peers over 2 weeks	Assessment 2 (surveys and observation)	KII
Incentives	\$15		\$14	\$15	\$15

Stakeholder Procedures – Key Informant Interviews:

Interested stakeholders will meet with a study team member remotely, using a secure video platform (e.g., Webex), or over the phone for a 30-minute semi-structured interview. The interview asks several questions about the acceptability of the program, any challenges, and potential room for changes/improvements. The interview will be recorded, and the recording will be transcribed.

Study details will be discussed prior to each interview. Stakeholder consent will be obtained orally prior to beginning the interview. Stakeholders will be informed that by participating in the interview/survey they are consenting to participate in the study. Stakeholders will be compensated \$30 for completion of the interview.

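### Section 3 lets the treating Peer administer the satisfaction, alliance and other questionnaires with no out-of-view rule, and Section 12's bar on Peer access is not reconciled with this

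*Combined protocol and SAP*

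**What the plan says.** On administration, Section 3 (Study Procedures) reads: "All assessments (including the questionnaires and videotaped interaction) will be administered by either a Peer or by study staff, depending on Peer availability". The choice between Peer and study staff depends on availability, not on who treated the parent.

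On delivery, Section 3 says that "the participant will take part in the EFT intervention, led by a trained peer parent or the PI". It later says that peer parents conduct the interventions, and it provides for 3 to 7 meetings with a peer over the following two weeks.

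On what is measured and when:
- After the session: "Immediately following the intervention, parents will complete the MCQ and Parenting Joy survey again". No administrator is named for this step.
- At the end: "At the last assessment only, parents will also complete a client satisfaction questionnaire (CSQ) and a Working Alliance Inventory (WAI". These two ratings have no baseline.
- The post-assessment repeats nearly all of the baseline self-reports.

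On setting and mode, Section 2 (Enrollment and/or Screening) says that "screening, consent processes, assessments and the intervention will be conducted in small, private rooms located at Odyssey House". Section 3 has questionnaires completed in REDCap on a password-protected computer; if that is impractical, "participants will be able to fill out forms using paper-and-pencil".

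On access, Section 12 (Data Analytic and Safety Monitoring Plan) denies community partners and peer parents access to assessment materials of any kind. The same section counts peer parents among the research staff and reserves data access to the research staff.

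**The concern.** A parent asked to rate the intervention and the working relationship may answer differently if the person being rated is administering the form or sitting in view. The plan allows that arrangement and has no rule that prevents it during completion.

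The CSQ and WAI are the most exposed. Satisfaction is named in Aim 1, and the findings are meant to guide revision of the intervention and a larger trial. With a single measurement, any shift stays in the score in full. The parent interview is the only other parent source on satisfaction. It is optional, and Section 3 does not say who conducts it.

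For measures taken before and after, a shift of equal size at both times cancels. Equality cannot be assumed, because a 75 to 90 minute session and the check-ins fall between the two assessments. The direction is open too: rapport could raise favourable answers, while the lower stigma that Section 3 attributes to peers could raise disclosure.

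**Working it through.** **Step 1. Compare the provisions.** The plan gives no figure on this point, so the main check is a reading of the text.

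| Question | What the text provides | Is the treating Peer kept out of view? |
|---|---|---|
| Who administers? | Peer or study staff, by Peer availability (Section 3) | No; study staff may be used, but not because of who treated the parent |
| Where? | Small private rooms (Section 2) | No; this protects against outsiders, not against the administrator |
| How? | Parent completes on computer or paper (Section 3) | No; nothing on whether the administrator leaves or can see the screen or form |
| Who may see materials? | Peer parents barred from assessment materials (Section 12) | Addresses access, not presence |

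Section 12's bar cannot be applied literally while Peers administer questionnaires under Section 3. It sits among storage and confidentiality rules and most naturally means completed materials, but it does not say so. Because Section 12 also counts peer parents as research staff, the group given data access, it is unclear on its own terms.

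**Step 2. Illustration of scale. Every shift below is assumed.** From the documents: at most n = 30 parents, and single-sided paired t-tests for self-reported parenting and, if appropriate, for consideration of future consequences. Assumed: n = 20 as a smaller sample; shifts d = 0.1, 0.2 and 0.3 SD; exposure of all or half of the parents; roughly normal scores with no ceiling; a 95% confidence interval for the CSQ and WAI means (the plan specifies none); one-sided alpha 0.05 (the plan states none).

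*Once-collected scores.* Half-width in SD units = t(0.975, n−1)/√n:
- n = 30: 2.045/√30 = 0.373
- n = 20: 2.093/√20 = 0.468

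Coverage of the shift-free mean = P(|T| < t(0.975, n−1)), where T is noncentral t with n−1 df and noncentrality d√n. At n = 30 and d = 0.2 the noncentrality is 0.2 × √30 = 1.095. If a random half are shifted, the mean shift is d/2 and the SD is √(1 + d²/4).

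| Exposed | n | d = 0.1 | d = 0.2 | d = 0.3 |
|---|---|---|---|---|
| All | 30 | 0.917 | 0.815 | 0.645 |
| All | 20 | 0.929 | 0.864 | 0.753 |
| Half | 30 | 0.942 | 0.918 | 0.877 |
| Half | 20 | 0.945 | 0.929 | 0.903 |

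By symmetry these hold for a shift in either direction.

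*Paired t-tests.* Rejection rate with no true change = P(T > t(0.95, n−1)), with d now in SDs of change.

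| Shift, n = 30 | d = 0.1 | d = 0.2 | d = 0.3 |
|---|---|---|---|
| Favourable, all parents | 0.134 | 0.283 | 0.484 |
| Favourable, half | 0.084 | 0.133 | 0.197 |
| Opposite, all parents | 0.0146 | 0.0033 | 0.0006 |

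An opposite shift would hide benefit. None of these figures applies to the benchmark that at least 50% of patients show decreased delay discounting.

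**The case against.** Four points weigh on the other side.

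1. A reader might infer that nothing in the plan prevents Peers from seeing answers. The documents do not support that: Section 12 contains an express bar. What remains is a conflict to reconcile, and silence about presence and visibility while forms are being completed. This objection stands and sets the limits of the point.
2. A reader might infer that the treating Peer will administer the CSQ and WAI. Section 3 says a Peer or study staff, so this is permitted, not required. Section 3 also provides for training and weekly supervision of Peers, and seating during self-completion is often settled in operating procedures. That lowers the likely exposure, but the written rule still allocates by availability.
3. Staff at hand serve a purpose. Section 4 encourages parents troubled by a questionnaire to talk to research staff and lets them skip items and still be paid. This is a reason to keep help nearby, not for the rated Peer to be in view.
4. The figures test an analysis that the plan does not contain for the CSQ and WAI, and small or partial shifts do little harm. This stands, so they are illustration only. The study is also a small case series with additional interview data, which limits the stakes.

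**Conclusion.** The point holds as a procedural weakness that should be corrected. Following Section 3 as written allows the rated Peer to administer the ratings of the intervention and the alliance. No available text keeps that Peer out of view, and Section 12's access bar is not reconciled with Section 3.

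The size is unknown. A reader might take the illustration as showing that satisfaction will be inflated or that the paired tests will give false positives. The documents support neither: they give no shift, no direction and no rate of same-Peer administration. The larger effects above need every parent to shift by 0.2 to 0.3 SD. Nor is the 50% delay discounting benchmark shown to be affected.

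The conclusion rests on the available text. The passage between the outcome paragraphs of Section 12 and Section 14 was not available and could contain a relevant rule. Private completion would remove one possible source of bias; it would not make up for the lack of a control group.

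**What to change.** 1. In Section 3, state that parents enter all questionnaires themselves in REDCap, or on paper with sealed return, out of the treating Peer's view. Apply this in the same way at Assessment 1, at the MCQ and Parenting Joy step after the session, and at Assessment 2, above all for the CSQ and WAI.
2. Where a parent needs help, prefer available non-Peer staff or a Peer who did not treat that parent, and record in REDCap who administered each assessment. Keep this as a preference so that no assessment is lost: the number of alternative staff on site is not given, and Section 3 notes that parents may leave without warning.
3. Reconcile Section 12 with Section 3: say whether the bar on peer parents covers completed materials and data only, and whether the research staff with data access include peer parents.

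The cost is wording, envelopes for paper forms and one REDCap field. No extra staff are needed. The downside is slightly less scheduling flexibility.
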